Population and patient selection criteria

A cohort of 100 adults (18-75 years) patients with UC, either naïve or under standard of care (both responders and non-responders to therapies) will be prospectively enrolled. In all cases, the Montreal classification, and the clinical and endoscopic indexes of activity will be carefully assessed. The control group consists of 100 sex- and age-matched subjects, selected in the same Center, undergoing colonoscopy as examination in the diagnostic algorithm for lower abdominal symptoms and **that results normal, thus confirming the diagnosis of** irritable bowel syndrome, and who were not taking drugs possibly affecting immune response and microbiota composition. **A small cohort of patients (n=20) suffering from microscopic colitis will be also enrolled as pathological control group.** All enrolled patients and controls will undergo lower endoscopy with mucosal sampling as **diagnostic** workup for their condition. Patients with active UC undergo colonoscopy and laboratory tests according to international

guidelines and depending on physician judgement. More in depth, active UC patients will undergo colonoscopy at baseline, while laboratory tests will be performed at baseline, and at 3 and 6 months. As optional follow-up, accordingly with physician evaluation, some patients will undergo medical examination and laboratory tests at 9 and 12 months, and colonoscopy at 12 months. The aim of the study is settled at 6 months, but adding the optional follow-up at 9 and 12 months, will aid us to understand if patients with EBV colitis undergo colectomy more frequently than patients without EBV colitis. Patients with UC in remission will undergo colonoscopy and laboratory tests according to ECCO-ESGAR guidelines [52]. Patients with suspicion of irritable bowel syndrome will undergo colonoscopy and laboratory tests if alarm features are present (aged >45-50 years, anemia, weight loss, familiar history of colon cancer, blood mixed in the stool). The exclusion criteria include: significant comorbidities, malignancy, pregnancy, organ failure, immunodeficiencies, active infections, recent abdominal surgery, or invalidating psychiatric-neurological disorders.

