5.2.2 Secondary endpoint

a- Comparison of the presence of EBV infection in the cohort of patients suffering from UC and divided into the following subgroups: a) new diagnosis; b) responders to conventional therapies; c) non-responders to conventional therapies, in order to unravel whether it is a bystander or causative of the onset/relapse of the disease and whether it is responsible for refractoriness to standard of care.

b- Evaluation of the diagnostic ability in detection of EBV infection of ISH performed on mucosal specimens with respect to qRealTime-PCR.

c- Evaluation of the diagnostic ability in detection of EBV infection between qRealTime-PCR performed on peripheral blood samples with respect to mucosal specimens.

d- Evaluation of association between mucosal/blood viral load and mucosal damage as endoscopically assessed (see paragraph 5).

e- Evaluation of association between clinical index of UC activity and EBV infection.

f- Evaluation of association between steroid therapy (absent, previous or current) and EBV infection.

g- Evaluation of association between immunosuppressive therapy (absent, previous or current) and EBV infection.

h- Evaluation of association between biological therapy (absent, previous or current) and EBV infection.

i- Evaluation of the prognostic role of EBV infection on the 6 and 12 months outcome (colectomy / number of hospitalization / cause of hospitalization).

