The **control group consists of 100 sex- and age-matched subjects**, selected in the same Center, undergoing colonoscopy with mucosal sampling as diagnostic workup for IBS in order to exclude macroscopic or microscopic disorders, or because alarm features are present: aged > 45-50 years, anemia, family history of colon cancer. That are confirmed to be suffering from IBS (C1), functional constipation/diarrhea (C2, C3) and functional abdominal bloating/distension (C4), following the Rome IV criteria (48), and who were not taking drugs possibly affecting immune response (steroids, immunosuppressant and biological agents) and microbiota composition (antibiotics, probiotics, prebiotics, proton pump inhibitors).

In addition, a small cohort of patients (n=20) suffering from **microscopic colitis** will be also enrolled as pathological control group (49).

All enrolled patients and controls undergo lower endoscopy with mucosal sampling and laboratory tests as diagnostic workup for their condition:

- Patients with active UC undergo colonoscopy and laboratory tests according to International guidelines and depending on physician judgement: active UC patients will undergo colonoscopy at baseline and laboratory tests at baseline, and at 3 and 6 months. A number of these patients, according to medical judgment, undergo medical examination at 9 and 12 months, and laboratory tests and colonoscopy at 12 months as optional follow-up. This is why the aim of the study is calculated at 6 months, but adding the optional follow-up at 9 and 12 months, will aid to understand if patients with superimposed EBV colitis undergo colectomy more frequently than patients without EBV colitis
- Patients with UC in remission undergo colonoscopy and laboratory tests as standard follow-up of their pathological condition according ECCO-ESGAR guidelines [52] (ex: to evaluate mucosal healing or screening)
- Patients with IBS undergo colonoscopy and laboratory tests only if alarm features are present (age > 45-50 years, anemia, family history of colon cancer, weight loss, blood mixed with stool).

Each enrolled case will undergo clinical and/or laboratory examination as standard follow-up of his/her pathological condition. All the laboratory tests are shown in the Appendix 5.

Each patient and control give written informed consent after approval by the local Bio-Ethics Committee is obtained.

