l) The Informed Consent Form will include a statement by which the patient allows the Sponsor's duly authorised personnel, the IEC, and the regulatory authorities to have direct access to source data which supports the data on the eCRF (e.g., patient's medical file, appointment books, original laboratory records, etc.). These personnel, bound by professional secrecy, will not disclose any personal identity or personal medical information.

m) Data collection and study report form monitoring. All data obtained for this study will be entered into a regulation compliant Data Management System. Data will be recorded with an Electronic Data Capture system using eCRFs. Specifically, the Electronic Data Capture system will be based on the IGIBDReg platform. IGIBDReg is a novel workflow methodology and software tool that expedites the electronic collection of research data from a single site or multi-site clinical research study. The study database will be resident on OVH server (<https://www.ovhcloud.com/>) as required by European Certification

n) Procedure to account for missing or spurious data. In case of missing clinical assessment at follow-up visit, the last observation carried forward from the latest earlier visit will apply, while in case of missing clinical, endoscopic and histologic data by month 12, the evaluation of outcome will not be possible. We expect to have 10% patients on drop-out. IGIBDReg provides section to recording missing or N/A information.

o) Procedure to account for protocol deviations. Generally, a protocol deviation is not imperative for patient withdrawal. Before the statistical analysis begins, the protocol deviations must be taken into account for the analysis. The mandatory withdrawal reasons will be considered as major protocol deviations. Other protocol deviation will be classified as minor protocol deviation. Additionally, the lack of compliance with any of the inclusion/exclusion criterion, either identified before or after enrolment into the study, will be considered as major protocol deviation. Any protocol deviation must be recorded in the eCRF (specific section in IGIBDReg). Once the study has begun, any modification of the protocol deviation will be specified in the statistical analysis plan. This will be done before closing the database.

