Annex 2: eCRF

Annex 3: Budget REBUC

Annex 4: Lista Centri REBUC

Appendix 1

SCCAI: Simple Clinical Colitis Activity Index

Variabile	Punteggio				
	0	1	2	3	4
Numero di scariche diurne	1 - 3	4 - 6	7 - 9	>9	
Numero di scariche notturne		1 - 3	4 - 6		
Urgenza di defecare		di corsa	immediatamente	incontinenza	
Presenza di sangue nelle feci	assente	tracce	occasionale	sempre	
Valutazione clinica globale	molto bene	lievemente al di sotto della normalità	scadente	pessima	terribile
Manifestazioni extraintestinali (1 punto per ciascuna manifestazione)					
Score totale					

Appendix 2

UCEIS: Ulcerative Colitis Endoscopic Index of Severity

Variabile	Punteggio				
	1	2	3	4	5
Pattern vascolare	normale		perdita a chiazze		obliterato
Eritema mucosale	assente		lievemente arrossata		molto arrossata
Superficie mucosale	normale		granulare		nodulare
Edema mucosale	assente		probabile		definito
Presenza di muco-pus	assente		poco		tanto
Presenza di sangue	assente	mucosale	luminale lieve	luminale moderato	luminale severo
Fragilità mucosale	assente	lieve	moderata	severa	molto severa
Fragilità mucosale al contatto	assente		probabile		definita
Presenza di erosioni-ulcere	assenti	presenza di erosioni	presenza di ulcere superficiali	presenza di ulcere profonde	
Estensione di erosioni-ulcere	assente	limitata	sostanziale	estesa	
Score totale					

Appendix 3

Schedule assessments in active UC

	Screening	Baseline	Mandatory follow-up		Optional follow-up	
			3 months	6 months	9 months	12 months
Clinical assessment	X		X	X	X	X
Body Mass Index		X	X	X	X	X
Diagnosis confirmation	X					
Clinical index of activity		X	X	X	X	X
Laboratory analyses		X	X	X		X
Blood sampling		X	X	X		X
Lower endoscopy		X				X
Endoscopic index of activity		X				X
Mucosal sampling		X				X
Histology examination		X				X
Immohistochemistry		X				X
ISH		X				X
Viral load assessment		X				X

Appendix 4

Schedule assessments in UC in remission and IBS

	Screening	Baseline
Clinical assessment	X	
Body Mass Index		X
Diagnosis confirmation	X	
Clinical index of activity		X
Laboratory analyses		X
Blood sampling		X
Lower endoscopy		X
Endoscopic index of activity		X
Mucosal sampling		X
Histology examination		X
Immunohistochemistry		X
ISH		X
Viral load assessment		X

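### Section 10 n) makes outcome evaluation depend on month-12 endoscopic and histologic data that are optional and that the colectomy and hospitalisation endpoint does not need

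*Protocol*

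**What the plan says.** Section 10 n) has two rules. For a missed visit: "In case of missing clinical assessment at follow-up visit, the last observation carried forward from the latest earlier visit will apply". For month 12: "in case of missing clinical, endoscopic and histologic data by month 12, the evaluation of outcome will not be possible". The same paragraph expects 10% drop-out.

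Month 12 is not a required visit. Section 6 says of patients with active UC: "A number of these patients, according to medical judgment, undergo medical examination at 9 and 12 months", with the month-12 colonoscopy also optional. The Summary likewise says that "some patients will undergo medical examination and laboratory tests at 9 and 12 months, and colonoscopy at 12 months". Section 15 describes 6 months of mandatory and 6 months of facultative follow-up. In Appendix 3, endoscopy, mucosal sampling and histology appear only at baseline and at the optional month 12; the mandatory visits at months 3 and 6 include none of them. Appendix 4, headed "Schedule assessments in UC in remission and IBS", has screening and baseline columns only.

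The endpoint concerned is 5.2.2 i: "Evaluation of the prognostic role of EBV infection on the 6 and 12 months outcome", meaning colectomy and the number and cause of hospitalisations. Section 8.2 assigns Cox regression to colectomy and hospitalisation, and Poisson regression to the number of hospitalisations.

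**The concern.** A data set that the schedule leaves to the physician is made a condition for evaluating outcome. The condition also does not suit the endpoint. Colectomy and hospitalisation are dated events found in medical files; a Cox model censors at last contact and a Poisson model uses person-time. Neither needs a month-12 biopsy.

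Two kinds of patient are at risk of being dropped. One has completed everything mandatory and was not selected for the optional visit. The other had a colectomy before month 12 and may no longer be able to have the scheduled colonoscopy and mucosal sampling; the rule makes no exception for this patient. The Summary and Section 6 say that the optional follow-up is there to help show whether patients with EBV colitis have more colectomies, so the rule can work against its stated purpose.

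**Working it through.** **1. What the rule does under each reading.** The wording does not say whether one missing data type is enough or all three must be missing, nor whether data from before month 12 count.

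| Patient | Any one type missing at month 12 | All three missing at month 12 | Earlier data count |
|---|---|---|---|
| Completed months 3 and 6, no optional visit | not evaluable | not evaluable, unless a carried-forward clinical assessment counts as present | evaluable |
| Colectomy at month 4, seen clinically at month 12, no colonoscopy or mucosal samples | not evaluable | evaluable | evaluable |
| Colectomy at month 4, no month-12 visit | not evaluable | not evaluable, same proviso | evaluable |

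Under the last column the rule would hardly ever operate, because Section 9 already withdraws patients from whom no mucosal biopsies can be taken. A second ambiguity is whether the rule limits only the 12-month outcome or the 6-month outcome as well.

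**2. How many patients could reach month 12.** Inputs from Section 15: recruitment 29 months, minimum participation 7 months, whole study 36 months, 32 months from first enrolment. The plan's own total reproduces: 29 + 7 = 36. That sum leaves no room for 12 months of follow-up in late recruits. The Summary's dates (30.10.2022 to 30.05.2025) give about 31 months of data collection.

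Assuming uniform accrual over the 29 months, the share that can reach month 12 is (window − 12)/29:

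- 31 months: 19/29 = 66%
- 32 months: 20/29 = 69%
- 36 months: 24/29 = 83%

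So 34%, 31% or 17% could have no month-12 data for calendar reasons alone, before optional attendance is considered.

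**3. Illustration of the strict reading.** The protocol gives no colectomy rate or month-12 attendance, so these inputs are assumed: 100 UC patients, 30 EBV-positive with 12-month colectomy risk 20%, and 70 EBV-negative with risk 5%.

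- Everyone kept: 30 × 0.20 = 6 and 70 × 0.05 = 3.5, total 9.5 colectomies; risk ratio 0.20/0.05 = 4.0.
- No colectomised patient has month-12 samples: 0 events kept; no ratio can be estimated.
- Half of the colectomies kept: 3 + 1.75 = 4.75 events. The non-colectomised number 24 and 66.5. With attendance a among EBV-positive and b among EBV-negative patients who kept their colon, the ratio is [3/(3 + 24a)] / [1.75/(1.75 + 66.5b)].

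| a | b | Risks kept | Risk ratio |
|---|---|---|---|
| 90% | 90% | 3/24.6 and 1.75/61.6 | 4.3 |
| 70% | 70% | 3/19.8 and 1.75/48.3 | 4.2 |
| 80% | 40% | 3/22.2 and 1.75/28.35 | 2.2 |
| 40% | 80% | 3/12.6 and 1.75/54.95 | 7.5 |

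The loss of events comes from the rule. The distortion of the ratio comes mainly from attendance that differs by EBV status, which is assumed here.

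**The case against.** The strongest reply is that the rule lists three data types joined by a conjunction and speaks of data by month 12. On a lenient reading a colectomised patient with baseline endoscopy and histology and a recorded operation is not missing all three, and nothing is lost. The rule may also limit only the 12-month outcome, while the Summary and Section 6 set the study's aim at 6 months. Both points stand so far as they go: loss of colectomies is possible, not certain. They do not remove the conflict with the optional schedule, and wording that decides who is analysed should not be open to this choice.

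A reader might infer three stronger things that the protocol does not support.

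- That the prognostic result will be biased. Discretionary attendance does not show that attenders are sicker or that attendance depends on EBV status. When attendance is equal in step 3, the ratio hardly moves and the harm is lost events.
- That carrying the last observation forward sets event status to no event. That rule is worded for a missing clinical assessment, and Section 8.2 gives the events to Cox regression.
- That events in UC patients in remission go unrecorded. Appendix 4 has no follow-up columns for them, but Section 6 mentions standard follow-up for every enrolled case, Section 15 states the mandatory 6 months without limiting it to active disease, and Section 7.1 gives outcome monitoring to the local investigator. These passages need reconciling; they do not show that events are missed.

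**Conclusion.** The conflict holds. Section 10 n) ties outcome evaluation to data that the Summary, Section 6, Section 15 and Appendix 3 make optional and that endpoint 5.2.2 i does not require. On the strict reading it removes patients who did everything mandatory and can remove colectomised patients, leaving the 12-month prognostic analysis open to selection on physician judgment and on the outcome. Under uniform accrual, the timetable alone would leave 17% to 34% without month-12 data. The size and direction of any bias in the association with EBV cannot be derived from the protocol; the risk ratios above rest on assumed risks and attendance.

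This should be fixed, but it concerns one secondary endpoint. Baseline prevalence, the primary endpoint and the basis of the sample size, is unaffected.

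**What to change.** - In Section 10 n), restrict the month-12 completeness rule to analyses that use endoscopic or histologic data.
- For endpoint 5.2.2 i, take dated colectomies and hospitalisations from medical records for all followed UC patients, whether or not the optional visit takes place. Count a colectomy as an event whatever endoscopy or histology is available.
- Censor the Cox analyses at last contact and use person-time as the exposure in the Poisson model.
- State that last observation carried forward does not apply to event status.
- Reconcile Appendix 4 with Sections 6 and 15, so that it is clear which UC patients contribute to this endpoint.

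The cost is a wording change and a small amount of record checking. Section 10 d) already lists clinical charts and medical files as source data, and no visit or procedure is added.

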11 ETHICAL CONSIDERATIONS

11.1 Patient protection

Both the Principal Investigators and the Study Coordinator will ensure that this study is conducted in agreement with either the Declaration of Helsinki (Tokyo, Venice, Hong Kong and Somerset West amendments) and the Italian laws and regulations (Appendix 6).

The protocol has been written, and the study will be conducted according to the ICH Guideline for GCP. The protocol and its annexes are subject to review and approval by the competent Independent Ethics Committee(s) (IEC). All correspondence with the IEC will be retained in the Investigator Site File.

11.2 Subject identification – Personal Data protection

All records identifying the subject will be kept confidential and, to the extent permitted by the applicable laws and/or regulations, not be made publicly available. The name of the patient will not be asked for nor recorded at the Data Center. A sequential identification number will be automatically attributed to each patient registered in the study. This number will identify the patient and must be included on all case report forms.

Any and all patient information or documentation pertaining to this study, to the extent permitting, through a “key” kept anywhere, regardless of whether such key is supplied along with the information or documentation or not, must be considered as containing sensitive personal data of the patient, and is therefore subjected to the provisions of applicable data protection (“privacy”) regulations. The Study Coordinator and all the Principal Investigators will be aware that a breach of such regulations may result in administrative or even criminal sanctions.

An information sheet prepared according to such regulations and a form to evidence the consent of patients to the processing of such data will accompany the informed consent administered to the patient (see Annex no. 1). Such information must (i) identify the roles of the holder and processor (appointed by the holder) of the patient personal data (also if not directly identifying the patient), as well as the purposes of the personal data collection and processing (scientific research), (ii) adequately describe the flows of communication involving them, particularly if third parties should become involved, and (iii) seek the patient's prior and specific consent to such processing.

In addition, anonymized data may be uploaded, with explicit consent, on a single database protected by password that can be accessed through the platform of the IGBD database. The members of the IG-IBD Scientific and Steering Committee and the Investigators who coordinate this study will have access to the database; access and consultation of the data will be carried only for scheduled review or on the specific mandate of the IGBD Scientific Committee for the timely assessment of specific variables.

3. Data Protection & Patient Confidentiality

All investigators and study site staff involved in this project comply with the requirements of the "Regolamento Generale sulla Protezione dei Dati" (usually known as GDPR) of 25th May, 2018, referring to the Regulation of the United Europe no. 2016/679, with regards to the collection, storage, processing and disclosure of personal information. An electronically generated code will be assigned to each case whose identity will be known only at the clinician who has in charge the patient and her/his staff. Each site is responsible for keeping an updated list of patients with their codes. This is to protect the anonymity of the collected data. The Study Coordinator guarantees that only pseudo-anonymized data will be received and recorded at each site. Moreover, only pseudo-anonymized data will be shared with the study team and other investigators.

All information obtained as a result of this study will be considered confidential until the Steering Committee deems it appropriate. This confidential information will be the property of both the Study Coordinator and the Principal Investigators who has in charge the patient and must not be disclosed to third parties without prior written consent from the patients, and must only be used for the study purposes.

To protect patients' privacy, the Informed Consent Form will include a statement by which the patient allows the authorized personnel, the IEC, and the regulatory authorities to have direct access to source data that supports the data on the eCRF. These personnel, bound by professional secrecy, will not disclose any personal identity or personal medical information.

11.3 Informed consent

All patients will be informed of the aims and possible risks of the study. They will be also informed as to the strict confidentiality of their data, but that their medical records may be reviewed for study purposes by authorized individuals other than their treating physician. The patient informed consent is given as an annex to this protocol and will be prospectively approved by the IEC.

It is emphasized that the participation is voluntary and that the patient is allowed to refuse further participation in the protocol whenever she/he wants. This will not prejudice the patient's subsequent care. Documented informed consent will be obtained for all patients included in the study before they are registered at the Data Center. This will be done in accordance with the Italian regulatory requirements and the procedure will be compliant with the ICH guidelines on GCP. This implies that "the written informed consent form should be signed and personally dated by the patient or by the patient's legally acceptable representative" and by the Principal Investigator. The Study Coordinator will retain the original of each patient's signed informed consent form and a copy is given to the participant. Should a patient require a verbal translation of the study documentation by a locally approved interpreter/translator, it is the responsibility of the local Principal Investigator to use locally official translators. Any change to the proposed informed consent form suggested by the Study Coordinator or Principal Investigators must be agreed to by the Steering Committee before submission to the IEC of the Coordinator Centre, and a copy of the approved version must be provided to each Centre and the Data Manager after IEC approval. Any new information which becomes available and which might affect the patient's willingness to continue participating in the trial will be communicated to the patient as soon as possible verbally over the telephone where an additional visit will be arranged.

